10. SAFETY

Safety will be assessed by examination of adverse events, physical examination findings, vital signs, clinical laboratory measurements, antibodies to study drug and 12 lead ECGs. These results will be presented for the Safety Population by treatment group and overall.

10.1. Adverse Events

Adverse events will be coded by preferred term (PT) and system-organ-class (SOC) using the latest version of the Medical Dictionary for Regulatory Activities (MedDRA). All AE data will be presented in data listings.

Treatment Emergent Adverse Events.

Treatment-emergent AEs (TEAEs) will be summarized by treatment and overall, as well as by severity and relationship to study drug. TEAEs are defined as any AE that is not present before exposure to study drug or any AE already present that worsens in severity after exposure to study drug.

All summary tables, except from the overall summary table and summary by relationship to ticagrelor, will be based on TEAEs. Frequency and percentage at subject level as well as number of events will be presented in the summaries. The SOCs will be displayed in descending order of overall frequency and then alphabetically. The PTs will be displayed in descending order of overall frequency and then alphabetically within SOC. A subject with 2 or more AEs within the same level of summarization will be counted only once for subject counts in that level using the most severe (for the severity table) or most related (for the relationship to study drug table) incident.

Summary tables will be presented by treatment groups. Percentages will be based upon the number of subjects in the Safety Population overall and within each treatment group.

Incidence of Adverse Events

All AEs will be presented in a data listing, and all TEAEs will be presented in a summary table by SOC, PT, treatment group and overall. Additional table of TEAEs will be presented in a summary by PT only.

An overall summary table will be created with following categories:

- Any AE
- Any ticagrelor-related AE
- Any TEAE
- Any study-drug-related TEAE
- Any severe study-drug-related TEAE
- Any serious adverse event (SAE)
- Any treatment-emergent, study-drug-related SAE
- Any AE leading to early study discontinuation
- Any Infusion Site Reactions (ISR)

- Any death

For the purpose of above summary, a study-drug-related AE is an AE with definite, probable, possible, or missing relationship to the study drug on eCRF.

Relationship to Adverse Event

The relationship of AE to study drug or ticagrelor will be classified by the Investigator as unrelated, possible, probable, and definite. Treatment-emergent AEs will be summarized by SOC, PT, and relationship to study drug; AEs will be summarized by SOC, PT, and relationship to ticagrelor. A subject with 2 or more TEAEs within the same level of summarization will be counted only once in that level using the most related incident.

Severity

The severity (or intensity) of an AE refers to the extent to which it affects the subject's daily activities and will be classified as mild, moderate, or severe. The TEAEs will be summarized by SOC, PT, severity (including category 'Missing' for events with missing severity assessment on eCRF) and treatment group. A subject with 2 or more TEAEs within the same level of summarization will be counted only once using the most severe event.

Infusion Site TEAEs

The Infusion site assessments will be performed for all subjects within 15 minutes before initiation of PB2452 (or placebo) infusion at Hour 0, 1, 3, 24, and 48 hours after initiation of PB2452 (or placebo) infusion, and on Day 7. Infusion site reactions will be assessed according to the CTCAE v5 grading scale and will be recorded as AEs and included in the AE listings.

Serious Adverse Events

An AE or suspected adverse reaction is considered a SAE if, in the view of either the investigator or Sponsor, it results in any of the following outcomes

- Death
- Life-threatening AE
- Inpatient hospitalization or prolongation of existing hospitalization
- Persistent or significant incapacity or substantial disruption of the ability to conduct normal life functions
- Congenital anomaly or birth defect

All SAEs including deaths will be presented in a data listing.

Adverse Events Leading to Early Discontinuation

All SAEs and TEAEs leading to discontinuation of study drug will be presented in the data listings.

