5.1 Definitions

Subjects officially enter the Screening Period following provision of signing an informed consent (written or verbal).

A screen failure is a consented subject who has been deemed ineligible based on 1 or more eligibility criteria or who has withdrawn consent prior to treatment assignment.

Screen failures may be rescreened upon confirmation with Sponsor. Screen failures may be rescreened once, upon review and confirmation from the Sponsor. For examples, subjects that have out of range laboratory results and vital sign measurements may have repeat assessment(s) during the Screening period.

An enrolled subject is one who has provided written or verbal informed consent.

A randomized subject is one who has been randomized to a treatment group on Day 1.

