9.3.3 Population Analysis

9.3.3.1 Disposition

Subject disposition will be presented for all screened subjects, including number of screen- failed subjects and number of subjects randomized (all subjects).

Number and percentage of subjects in the following categories will be summarized as appropriate:

- Screen failed
- Enrolled
- Enrolled, but not randomized
- Randomized
- mITT population
- Safety population
- Per-Protocol population
- PK population

Additionally, a summary on study completion status and treatment completion will be presented along with reasons for discontinuation if any.

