4.2. Sample Size Justification

Approximately 200 subjects 50-80 years old inclusive will be enrolled across US or, if needed, other countries at 5-15 sites. The subjects will be randomized in a 3:1 ratio receiving either the

PB2452 investigational study drug or placebo. Hence, a total of approximately 150 subjects will be receiving PB2452 and approximately 50 subjects will be receiving placebo.

The primary efficacy endpoint will be assessed by comparing the minimum % inhibition of PRU assessed by VerifyNow within 4 hours after the initiation of study drug between PB2452 group vs placebo group. A sample size of approximately 200 subjects with 3:1 allocation ratio (PB2452:placebo) will provide > 99% power to detect a mean difference of 15 in % inhibition of PRU between PB2452 and placebo group using a two-sided two-sample t-test with type I error of 0.05 (a standard deviation of 20 for % inhibition is assumed within each treatment group, which is obtained from previous studies). The sample size of 200 (150 active vs 50 placebo) will provide substantial safety information on PB2452 in older and elderly healthy subjects.

Subjects who withdraw from the study and who do not have adequate collection of safety, hemodynamic and pharmacokinetic samples for evaluation of safety, PK, and PD profiles may be replaced at the discretion of the Sponsor. Any replacement subject will be assigned to receive the same treatment as the subject he or she is replacing.

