5. ANALYSIS POPULATIONS

The results from this study will be presented using the following populations: For purposes of analysis, the following populations are defined:

Population	Description
All Subjects	All subjects who sign the Informed Consent Form (ICF).
Intention-to-Treat Population	All randomized subjects.
Modified Intention-to-Treat Population	Modified Intention-to-Treat (mITT) population includes all subjects randomly assigned to study treatment, who take any amount of study drug (PB2452 or placebo). Subjects will be analyzed as treated.
Safety Population	The Safety Population includes all subjects who have received any amount of study drug (PB2452 or placebo). The Safety Population will be analyzed for all safety assessments. Subjects in the Safety population will be analyzed as treated.
Per Protocol Population	The Per Protocol (PP) population includes subjects in the mITT Population who do not have major protocol deviations and who complete the study. Protocol deviations will be assessed prior to database lock and unmasking. The PP population will be analyzed using observed data only for efficacy variables. Subjects in the PP population will be analyzed as treated.
PK Population	The PK population includes all subjects with a measurable PK sample of the study drug. The PK population will be used to summarize all PB2452 blood concentrations. Subjects in the PK population will be analyzed as treated.

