7. SUBJECT DISPOSITION

7.1. Disposition

Subject disposition will be presented for all screened subjects, including number of screen-failed subjects, number of subjects enrolled (i.e. receiving ticagrelor) and number of subjects randomized. For number of subjects randomized, subject disposition will be presented by randomized treatment group and total.

Number and percentage of subjects in the following categories will be summarized as appropriate:

- Screen failed
- Randomized (ITT Population)
- mITT Population
- Safety Population
- Per-Protocol Population
- PK Population

Additionally, a summary of study completion and treatment completion status will be presented along with reasons for discontinuation if any.

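### The ticagrelor-related adverse event tables leave out subjects who took ticagrelor but were never infused, so the tabulated rate is conditional on reaching infusion

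*SAP*

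**What the plan says.** - **Who is in the safety tables.** SAP 5: "The Safety Population includes all subjects who have received any amount of study drug (PB2452 or placebo"). Protocol 9.2.2 has the same rule, and Protocol 7 limits the term study drug to PB2452 or placebo. SAP 10 presents safety results for this population, and SAP 10.1 adds: "Percentages will be based upon the number of subjects in the Safety Population overall and within each treatment group".
- **Which events are in scope.** SAP 10.1 bases its summary tables on treatment-emergent events, with two exceptions: the overall summary table and the summary by relationship to ticagrelor. For the latter, "AEs will be summarized by SOC, PT, and relationship to ticagrelor". The overall table has a row for ticagrelor-related events.
- **When subjects can drop out.** Ticagrelor begins on the morning of Day -2. Protocol 6.1 reconfirms eligibility on Day -1. On Day 1, before randomization, it reviews the Day -1 laboratory results and the Day 1 vital signs.
- **What such subjects are called.** Protocol 5.1: "A screen failure is a consented subject who has been deemed ineligible based on 1 or more eligibility criteria", or one who withdraws consent before treatment assignment. It makes no exception for subjects already given ticagrelor.
- **Enrolled.** In Protocol 5.1 an enrolled subject is one who has consented. SAP 7.1 plans to report the "number of subjects enrolled (i.e. receiving ticagrelor").

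**The concern.** The two exemptions from the treatment-emergent rule make sense only if the SAP wants to describe events on ticagrelor before infusion. The denominator then removes every subject whose course ended before infusion, and that removal may depend on the outcome being counted. Active bleeding is an exclusion criterion, as are QTcF above 450 msec, a pause above 3 seconds, and a resting heart rate below 50 (Protocol 5.3). The ECG criteria apply explicitly on Day 1.

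The ticagrelor-related rate therefore describes subjects who came through pretreatment well enough to be infused, not everyone who was given ticagrelor. The same applies to the other rows of the overall table that are not limited to treatment-emergent events: any adverse event, any serious event, any event leading to early study discontinuation, and any death. Protocol 2.1.5.1 names bleeding on aspirin and/or ticagrelor as a study risk, and Protocol 2.1.5 calls it very low. These tables are the natural summary evidence for that statement.

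**Working it through.** **The plan's own figure.** The only design figure to reproduce is the power statement in SAP 4.2: 150 versus 50 subjects, SD 20, and a "two-sided two-sample t-test with type I error of 0.05", which "will provide > 99% power to detect a mean difference of 15 in % inhibition of PRU". The standard error is 20 × √(1/50 + 1/150) = 3.266, and 15/3.266 = 4.593. Power is about Φ(4.593 − 1.960) = 99.6%, or 99.5% with the noncentral t on 198 degrees of freedom. The figure reproduces. The present point does not depend on it.

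**Tracing one subject.** Take a subject who receives ticagrelor on Day -2 and Day -1, has an event, and is stopped before Hour 0 on Day 1.

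1. *Event collected?* Yes. Adverse events are recorded from consent (Protocol 8.1.2).
2. *Event of a type the two tables accept?* Yes. They are not limited to treatment-emergent events.
3. *Subject in the Safety Population?* No. No PB2452 or placebo was given.
4. *Counted in the tables?* No, by SAP 10 and 10.1. Neither document defines a ticagrelor-exposed population that would bring the subject back.

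The result is the same whether the subject is a screen failure under Protocol 5.1, is withdrawn by the investigator under Protocol 6.2.1.1, or is randomized but not infused.

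**How many.** Protocol 5 expects 250 to 300 screened for 200, so 50 to 100 are not randomized. How many of these stop after ticagrelor has started is not stated, and most may fail before Day -2.

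**Direction and size, under assumptions.** Let x of 200 Safety Population subjects have a ticagrelor-related event. Let m further subjects take ticagrelor without being infused, k of them with such an event. Then

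- tabulated rate = x/200
- rate among all exposed = (x + k)/(200 + m)

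The tabulated rate is too low exactly when k/m exceeds x/200. With x = 10 assumed (tabulated 5.0%):

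| m | all m had an event | half did | none did |
|---|---|---|---|
| 2 | 12/202 = 5.9% | 11/202 = 5.4% | 10/202 = 5.0% |
| 10 | 20/210 = 9.5% | 15/210 = 7.1% | 10/210 = 4.8% |
| 20 | 30/220 = 13.6% | 20/220 = 9.1% | 10/220 = 4.5% |

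The break-even case is 1 event among 20 omitted subjects: 11/220 = 5.0%. Because the exclusion criteria themselves pick out some events on ticagrelor, k/m above x/200 is the more plausible case. The documents do not establish it.

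**The case against.** The strongest reply is that no planned inference depends on this. The safety objective concerns PB2452 in ticagrelor-treated subjects, no endpoint estimates a ticagrelor event rate, and the Safety Population matches the protocol. That stands, and it limits the point to descriptive reporting. It does not remove it, because the SAP chose to plan a ticagrelor-relationship table and that table should describe the people exposed.

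Several stronger readings are tempting and are not supported:

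- *The events are lost, or pretreatment events appear only in listings.* Pretreatment events in subjects who went on to infusion are tabulated. Events in undosed subjects should be in the listings, since SAP 10.1 lists all adverse event data, although SAP 10 could be read as limiting safety output to the Safety Population. A listing gives no rate.
- *The SAP deleted a row that counted these subjects.* The protocol's "Enrolled, but not randomized" row (9.3.3.1) uses enrolled to mean consented, so it did not isolate ticagrelor-treated subjects. SAP 7.1 gives both the number receiving ticagrelor and the number randomized, and the difference is the count wanted. What is missing is an explicit row with reasons.
- *All of them are screen failures, so Protocol 5.1 must be rewritten.* An investigator withdrawal for an adverse event is not literally a screen failure, and the omission does not depend on the label.
- *Bradyarrhythmia is a main risk of pretreatment.* Protocol 2.1.5 and 2.1.5.1 do not name it. It can be inferred only from the heart-rate and pause criteria.

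**Conclusion.** The point holds as a reporting gap. By the SAP's own rules, the two summaries meant to reach back before infusion omit everyone who took ticagrelor and was not infused. The tabulated ticagrelor-related rate is conditional on reaching infusion and is likely, but not certain, to be too low.

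The size cannot be fixed from the documents, which give neither the number of such subjects nor a ticagrelor-related event rate. A reader might infer a definite understatement of several fold. For example, 4/200 = 2.0% against (4 + 10)/(200 + 10) = 6.7% is a 3.3-fold gap. That needs ten omitted subjects who all had such an event, so that 10 of 14 events (71%) led to removal in the roughly 48 hours of pretreatment. Nothing in the documents supports that, and if none of the omitted subjects had an event the table would be slightly too high.

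Nor should a reader infer bias between the arms. Subjects stopped before randomization belong to neither arm, so the randomized PB2452-versus-placebo comparison is not affected.

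**What to change.** In the SAP:

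1. Define a ticagrelor-exposed population: all subjects with at least one ticagrelor dose.
2. Use it, with a column for subjects not dosed with study drug and a total, for the relationship-to-ticagrelor table and for these rows of the overall table: any adverse event, any ticagrelor-related event, any serious event, any event leading to early study discontinuation, and any death.
3. Add a disposition row for subjects who received ticagrelor but were not randomized or not dosed, with reasons.
4. Reconcile enrolled between Protocol 5.1 (consented) and SAP 7.1 (receiving ticagrelor).
5. Keep the Safety Population for all PB2452-versus-placebo treatment-emergent tables.

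The protocol's screen-failure definition can stay as it is. The cost is one population flag, one extra table column, the disposition row and some wording. No new data are needed, since adverse events are collected from consent and SAP 7.1 already identifies ticagrelor recipients. SAP 2 treats analyses added after signing and database lock as post hoc, so the change belongs in the plan before then.

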10.2. Clinical Laboratory Assessments

Actual values and changes from baseline in clinical laboratory test results will be summarized by treatment at each time point using descriptive statistics (number of subjects, mean, SD, median, minimum, and maximum). Clinical laboratory test results will be presented in data listings as well.

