8.1.3 Classification of Events

8.1.3.1 Assessment of Severity

The severity (or intensity) of an AE will be determined by the Investigator and refers to the extent to which it affects the subject's daily activities. Severity will be classified as mild, moderate, or severe using the following criteria:

- Mild: These events require minimal to no treatment and do not interfere with the subject's daily activities
- **Moderate**: These events result in a low level of inconvenience or concern with the therapeutic measures. Moderate events may cause some interference with normal functioning
- Severe: These events interrupt a subject's usual daily activity and may require systemic drug therapy or other treatment. Severe events are usually incapacitating, life-threatening or fatal

Changes in the severity of an AE should be documented to allow assessment of the duration of the event at each level of intensity. An AE characterized as intermittent requires documentation of onset and duration of each episode. The CTCAE v5 grading scale will be used by the Sponsor to assess all AEs and laboratory abnormalities.

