8.4 Clinical Laboratory Findings

Clinical laboratory tests will be performed by MedPace Central Laboratory or local laboratory where applicable (i.e. Day -1). Blood and urine will be collected at the time points indicated in the Schedule of Events (Appendix 3) and will be prepared using standard procedures. Repeat clinical laboratory tests a t local or central laboratory may be performed at the discretion of the Investigator, if necessary, to evaluate clinical laboratory abnormalities, results of which are to be included in the electronic data capture system or eCRF. MedPace central laboratory will provide

the reference ranges for all clinical laboratory parameters where applicable. Study site will provide the clinical laboratory parameters for any local laboratory used.

Abnormal clinical laboratory values will be flagged as either high or low (or normal or abnormal) based on the reference ranges for each laboratory parameter. The Investigator will determine whether any of the abnormal high or low results are CS or NCS. Clinical significance is defined as any variation in results that has medical relevance and may result in an alteration in medical care (e.g., active observation, diagnostic measures, therapeutic measures). If a CS change from the Screening value is noted, the CS value and etiology or reason for clinical significance will be documented on the AE page of the eCRF.

The criteria for determining whether an abnormal test finding should be reported as an AE are as follows:

- Test result is associated with accompanying symptoms, and/or
- Test result requires additional diagnostic testing or medical/surgical intervention, and/or
- Test result leads to a change in study dosing or discontinuation from the study, or other therapy, and/or
- Test result is considered an AE by the Investigator or Sponsor

The Investigator will continue to monitor the subject with additional assessments until the values have reached either the reference range or the values at Screening or until the Investigator determines that follow-up is no longer medically necessary.

8.5 **Pregnancy and Contraception**

In enrolled female subjects who are of child-bearing potential (pre-menopausal), use of 2 effective birth control methods is required for 3 months after signing of the informed consent form. For definition of women of childbearing potential and of fertile men please refer to Appendix 2.

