10.3. Vital Signs

Actual values and changes from baseline in clinical laboratory test results will be summarized by treatment at each time point using descriptive statistics (number of subjects, mean, standard deviation [SD], median, minimum, and maximum). Vital signs (systolic blood pressure [SBP] and diastolic blood pressure [DBP], oral body temperature, respiratory rate, and heart rate [HR]) results will be presented in a data listing sorted by treatment group, subject, and collection date/time. Actual results and change from baseline will be summarized for the Safety Population.

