10.4. Electrocardiogram (ECG)

Twelve-lead ECGs will be obtained after the subject has rested in the supine position for ≥ 10 minutes or as clinically indicated based on reported AEs or laboratory findings, as necessary.

Electrocardiogram assessments will include comments concerning whether the tracings are normal or abnormal, rhythm, presence of arrhythmia or conduction defects, morphology, and any evidence of MI, or ST-segment, T-Wave, and U-Wave abnormalities. In addition, measurements of these intervals will be reported: HR, PR interval, QRS duration, QT interval, Fridericia-corrected QT interval (QTcF), and RR interval. The investigator will determine whether any of the 12-lead ECG results are CS or NCS.

If both QT and RR intervals are not missing, but QTcB interval is missing in the database the Bazett's-corrected QT interval (QTcB) measured in msec will be calculated using the formula below, where RR interval is measured in msec:

$$\bullet \quad QTcB = \frac{QT}{\sqrt{RR/1000}}$$

If both QT and RR intervals are not missing but QTcF interval is missing in the database, QTcF measured in msec will be calculated using the formula below, where RR interval is measured in msec:

$$\bullet \quad QTcF = \frac{QT}{\sqrt{RR/1000}}$$

Electrocardiogram results will be presented in data listing sorted by treatment group, subject, and date/time of assessment. Actual results and change from baseline will be summarized for the safety

population at each timepoint using descriptive statistics. All ECG results will be presented in a data listing.

In addition, subjects with outlying QTcF, and QTcB intervals (absolute value > 500 msec, absolute value > 480 msec, absolute value > 450 msec, or increase from baseline value >30 or >60 msec) will be listed in a separate data listing. A summary table will be presented for maximum QTcF and QTcB intervals (including scheduled and unscheduled assessments) meeting the outlying criteria using count and percentage.

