13. ANALYSIS CONVENTIONS

Post-text tables and listings will be prepared in accordance with the current ICH Guidelines. The information and explanatory notes to be provided in the “footer” or bottom of each table and listing will include the following information:

1. Date and time of output generation;
2. SAS® program name that generates the output;
3. Any other output specific details that require further elaboration.

In general, tables will be formatted with a column displaying findings for all subjects combined. Row entries in tables are made only if data exists for at least one subject (i.e., a row with all zeros will not appear). The only exception to this rule applies to tables that list the termination status of subjects (e.g., reasons for not completing the study). In this case, zeros will appear for study termination reasons that no subject satisfied. The summary tables clearly indicate the number of subjects to which the data apply and unknown or not performed are distinguished from missing data.

This section details general conventions to be used for the statistical analyses. The following conventions will be applied to all data presentations and analyses.

- All summary tables will include the analysis set sample size (i.e., number of subjects).
- Study Day 1 is defined as the first day the subject is exposed to the study drug. All *study days* are determined relative to the day of exposure to the study drug
- Baseline values will be defined as those values recorded closest to, but prior to, the first study treatment on Day 1 for all measurements except for PD/efficacy endpoints. For these endpoints baseline is the last value before ticagrelor is administered.
- Change from baseline will be calculated as follows:

$$\text{Change} = \text{Post-baseline value} - \text{baseline value}.$$

- Subject data obtained during unscheduled visits/assessments will not be summarized but will be included in subject data listings only; except for the determination of minimum % inhibition of PRU or PRI within 4 hours post-baseline. Unscheduled visit values will not be used to impute missing scheduled visit values, except for baseline calculation.
- No visit windows will be used to select efficacy data for analysis. Data collected at the nominal visit will be used for analysis (note that Day 35 is defined as 35 \pm 3, but will be reported as Day 35/End-of-study for simplification).

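### SAP 10.2 and 10.3 count a laboratory or vital-sign abnormality by arm only if it was recorded as an adverse event

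*SAP*

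**What the plan says.** **Planned output.** SAP 10.2 states: "Actual values and changes from baseline in clinical laboratory test results will be summarized by treatment at each time point using descriptive statistics". The statistics are number of subjects, mean, SD, median, minimum and maximum, and listings are added. Protocol 9.3.4.5 plans the same. For vital signs, SAP 10.3 closes with "Actual results and change from baseline will be summarized for the Safety Population" and plans a listing sorted by treatment group. Neither section plans a shift table, an out-of-range count, a count by grade, or a count of clinically significant findings.

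**Unscheduled values.** SAP 13 says: "Subject data obtained during unscheduled visits/assessments will not be summarized but will be included in subject data listings only". Its exceptions cover the minimum % inhibition of PRU or PRI and the baseline calculation. Protocol 8.4 allows repeat laboratory tests to follow up abnormalities, "results of which are to be included in the electronic data capture system or eCRF", so these values will be on file.

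**What is already classified.** Protocol 8.4: "Abnormal clinical laboratory values will be flagged as either high or low (or normal or abnormal) based on the reference ranges". Protocol 8.1.3.1: "The CTCAE v5 grading scale will be used by the Sponsor to assess all AEs and laboratory abnormalities". The investigator also judges the clinical significance of abnormal laboratory results and of vital signs (Protocol 8.4 and 6.1.1.5).

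**The ECG section differs.** SAP 10.4: "A summary table will be presented for maximum QTcF and QTcB intervals (including scheduled and unscheduled assessments) meeting the outlying criteria using count and percentage".

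**The concern.** Laboratory results and vital signs are named in the secondary safety endpoint (SAP 3.2). SAP 4.2 also presents the 150 versus 50 subjects as an important source of safety data. For these two data types, however, the only by-arm incidence tables are the adverse event tables of SAP 10.1. A value that was flagged or gradeable but not recorded as an adverse event adds to a mean and appears in a listing, and no table counts it. A reader who wants to know how many subjects per arm had, say, a grade 2 creatinine or a systolic pressure below 100 would have to count by hand, choosing the cut-off after unblinding.

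Unscheduled repeats, which are taken partly because something looked abnormal, are kept out of the summaries altogether. The ECG section shows that the authors saw the value of a worst-value count that includes unscheduled readings. They did not extend it to the other two data types.

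**Working it through.** The plan gives no figure on this point. The only design inputs are the arm sizes, 150 and 50 (SAP 4.2). All other inputs below are assumptions for illustration.

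**1. Which abnormalities are counted already.** Protocol 8.4 and 6.1.1.5 send clinically significant changes to the adverse event page. Protocol 8.4 also makes a laboratory result an adverse event if it comes with symptoms, leads to further testing or intervention, or changes dosing or other therapy. It adds the open criterion "Test result is considered an AE by the Investigator or Sponsor". Protocol 8.1.1 adds changes relevant to subject safety. SAP 10.1 then tabulates treatment-emergent events by arm. Values outside these routes have only SAP 10.2 and 10.3.

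**2. Can the planned statistics give the count?** Take 150 changes in SD units and hold n = 150, mean 0, SD 1, median 0, minimum -3.5 and maximum 3.0. Both sets below meet all six:

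| Set | Values (number of subjects) | Falls of at least 2 SD |
|---|---|---|
| A | -3.5 (1), -1.0 (4), -0.5 (63), 0 (69), 3.0 (13) | 1 (0.7%) |
| B | -3.5 (1), -2.0 (23), 0 (57), 0.5 (43), 1.0 (25), 3.0 (1) | 24 (16%) |

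- Sum A: -3.5 - 4 - 31.5 + 39 = 0. Sum B: -3.5 - 46 + 21.5 + 25 + 3 = 0.
- Sum of squares A: 12.25 + 4 + 15.75 + 117 = 149. B: 12.25 + 92 + 10.75 + 25 + 9 = 149. So the SD is √(149/149) = 1 in both.
- Ranks 75 and 76 are zeros in both, so the median is 0.

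On a 0.1 SD grid, 24 is the largest feasible count; 25 is infeasible. The planned statistics do not determine the number of subjects.

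**3. Would the mean show it?** If 5 of 150 subjects each rose by 3 SD, the arm mean would move by 5 × 3 / 150 = 0.10 SD. The standard error of the difference between arms is √(1/50 + 1/150) = 0.163 SD. The mean would not show those subjects. The maximum would show one of them.

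**4. How precise would the added counts be?** Clopper-Pearson 95% limits: 0/150 has an upper limit of 2.4%; 0/50 of 7.1%; 5/150 is 3.3% (1.1% to 7.6%). Two-sided Fisher tests: 5/150 versus 0/50 gives p = 0.33. The smallest PB2452 count with p below 0.05 is 12/150 (8.0%, p = 0.040) against 0/50, and 17/150 (11.3%, p = 0.048) against 1/50.

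**5. How large is the background?** There are eight scheduled post-dose vital-sign readings: 15, 30, 45 and 60 minutes, 24 and 48 hours, Day 7 and Day 35. As an example only, take a 30 mmHg systolic fall, normal changes with mean 0 and an assumed SD of 15 mmHg. The cut-off is 30/15 = 2 SD, or 2.3% per reading. For the worst of eight independent readings the chance is 1 - 0.97725^8 = 16.8%. With a common correlation ρ it is 1 - ∫ φ(z) Φ((2 - √ρ z)/√(1 - ρ))^8 dz, which gives 11.6% at ρ = 0.5 and 7.3% at ρ = 0.8. A worst-value count thus carries a background of roughly 7% to 17% in either arm under these assumptions.

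**The case against.** The strongest reply is that little is left uncounted: only values that blinded staff did not judge clinically significant and that met no other adverse event criterion. Protocol 8.1.1 can be read more widely still, with the safety-relevance wording qualifying only its last item. This stands, and it limits the point to the remainder.

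Second, the tabulated extremes carry information. If minimum and maximum stay inside a limit at every time point, the number of subjects crossing it on a scheduled reading is exactly zero. This also stands. It does not help once the count is above zero, and it does not cover unscheduled values.

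Third, no commitment is broken. SAP 10.2 carries out Protocol 9.3.4.5 as written, the endpoint promises monitoring and recording rather than rates, and SAP 2 allows further analyses labelled as such. True, so this is an improvement and not the repair of an error. Tables added later would, however, have limits chosen with the data in view.

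Fourth, set B is contrived. Its 24 low values sum to -49.5, so the other 126 subjects must average a rise of 49.5/126 = 0.39 SD. It shows that the statistics do not fix the count, not that a realistic signal would be hidden.

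A reader might infer that laboratory or vital-sign signals would go unseen, or that the comparison favours PB2452. The documents do not support either. Clinically significant changes are tabulated by arm, every value is listed, and adverse event reporting is blinded.

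**Conclusion.** The gap is real and limited. Laboratory and vital-sign abnormalities not recorded as adverse events are counted by arm in no planned table, and the planned statistics cannot supply the count: the same six statistics fit 0.7% or 16% of an arm. That result is arithmetic and needs no assumption about the trial's data. The background range of 7% to 17% does rest on an assumed SD of 15 mmHg, assumed correlations from 0 to 0.8 and an example criterion; it shows only that placebo rates must stand alongside.

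The added counts would describe and would rarely separate the arms, since 12/150 against 0/50 is needed. The efficacy conclusion is untouched. This is an inexpensive improvement worth making. It does not bear on the validity of the trial.

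**What to change.** - **SAP 10.2:** add a by-arm table of worst post-dose CTCAE v5 grade. Where no grade exists, show the low/normal/high shift from baseline using the existing flags. Include unscheduled values. Because Day -1 tests are local, classify each value against its own laboratory's range.
- **SAP 10.3:** add by-arm counts and percentages of subjects whose worst post-dose value, unscheduled readings included, is newly outside the Protocol 5.3 limits: systolic <100 or >160 mm Hg, diastolic <40 or >95 mm Hg, heart rate <50 or >100 bpm. These are eligibility limits, but they are already in the protocol and use the same 10-minute supine rest. The sponsor may fix other limits before unblinding.
- **SAP 13:** extend the exception for unscheduled values to both tables and, for consistency, to the QTc table in SAP 10.4, which already includes them.
- **Presentation:** show PB2452 and placebo side by side with 95% intervals, labelled descriptive. Keep all planned summaries, listings and adverse event tables.
- **Editorial:** the first sentence of SAP 10.3 refers to laboratory results where vital signs are meant.

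The data are already collected. The cost is two tables, a wording change, and agreement on limits before unblinding. Protocol 8.1.3.1 does not say that laboratory grades are stored, so they may have to be derived across the analytes in Protocol Table 2. Readers must also be warned not to take the background rate for a drug effect.
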